6.4 Post-Op Discharge

This form is to be filled out the morning after the patient's operation. This information is to be found in the patient's record which will be with the nurses in the ward.

1. Temporary Fixation using Damage Control

- a. Report whether or not temporary fixation was performed. If there is a mismatch between what was said about temporary fixation in the Intra-op/Randomize Form, warning messages will occur asking you to double check your answer.
- b. Note that if temporary fixation was not performed, the option to record the date of temporary fixation will not appear.

Temporary Fixation

Was damage control using a temporary external fixator performed? Yes No

* must provide value reset

The intra-operative form indicates that the patient **DID** require temporary fixation. Please review the patient's chart. Contact [name] if there is any confusion.

The intra-operative form indicates that the patient **DID NOT** require temporary fixation. Please review the patient's chart and contact [name] if there is any confusion.

What date was temporary fixation performed? Today D-M-Y

* must provide value

Format is DD-MM-YYYY. Insert date manually, by clicking on the calendar image above, or press "Today" if applicable

2. Date of definitive treatment

- a. This is a critical study question because the reports for follow-up visits is based on this question
- b. If there is a mismatch between the type of definitive option stated in this form and what the patient was randomized to, a warning message will appear
- c. The size of the interlocking screws does not have to be recorded.

Definitive Treatment	
Date of Definitive Operation	   <small>Format is DD-MM-YYYY. Insert date manually, by clicking on the calendar image above, or press "Today" if applicable</small>
This is a key study question <small>* must provide value</small>	
What type of definitive operation was performed?	
This is a key study question <small>* must provide value</small>	
The incorrect operation was performed. Please notify the review committee immediately.	
The incorrect operation was performed. Please notify the review committee immediately.	
What is the size of the SIGN nail used?	
Number of proximal interlocking screws	 1  2 
Number of distal interlocking screws	 1  2 
What is the training level of the most experienced surgeon present for the operation	 Consultant  Specialist  Resident  Registrar  Intern 

3. Operation duration times can be found in the patient's record. These have been recorded during the operation

Definitive Treatment Operation Duration	
Start of Preparation in OT	  
Patient Arrival in OT	  
Starting Time of Operation (Cut)	  
End Operation Time (Bandage)	  
End of Post-Op Preparation	  

4. Associated Orthopaedic Injuries and Injury Severity Score

- Review the information in the patient's record and note any other injuries that the patient has besides the open tibia fracture. If there are other injuries, check yes for the appropriate injury classification. A text box will appear. Record what the physician wrote word for word. It is best not to interpret what the doctor said.
- If there is something you see that the patient has but the physician did not record the associated injury, notify the physician to confirm. If the physician agrees, record the information in the patient's record first, then record in REDCAP.
- "Ipsilateral" means the same side of the body. "Contralateral" means the opposite side of the body. If a patient has a tibia fracture on the left leg, contralateral limb injuries refer to injuries on the right leg or arm

d. The Injury Severity Score uses a formula that turns diagnoses into a severity, and calculates the score over the entire body. It is an overall measure of the patient's health after an injury.

Associated Orthopedic Injuries			
	Yes	No	
Other IPSILATERAL LOWER extremity injuries (besides the open tibia fracture)?			reset
Any CONTRALATERAL LOWER extremity injuries?			reset
Any IPSILATERAL UPPER extremity injuries?			reset
Any CONTRALATERAL UPPER extremity injuries?			reset
Describe other ipsilateral lower extremity injuries			Expand

Injury Severity Score			
	Yes	No	
Head/Neck (+ Cervical Spine)			reset
Face (+ Facial Skeleton, Nose, Mouth, Eyes, Ears)			reset
Chest			reset
Abdomen (+ Lumbar Spine)			reset
External			reset
Describe head/neck injuries			Expand

5. Antibiotics Check

a. Record any additional antibiotics that were given in the ward and whether or not all the courses of antibiotics the patient was started on were properly completed (all doses were given on time)

Antibiotics Check

Did the patient get started on any other antibiotics while in the ward besides the ones that have already been recorded?

Yes
 No

* must provide value reset

What other antibiotics did the patient receive?

- Type of antibiotic
- Dose
- Timing

Expand

Were all antibiotic courses administered on time and completed?

Yes
 No

This is a key study question

* must provide value reset

Describe which antibiotics were not administered on time or completed.

Expand

Standard Study Antibiotics Regiment

- None or Mild Wound Contamination: Ceftriaxone (1g every 24hr for 2 days)
- Moderate: Ceftriaxone (as above) + Gentamycin (80mg every 12hr for 2 days)
- Severe or High-Risk: Ceftriaxone + Gentamycin (as above) + Metronidazole (500mg every 8hr for 2 days)

b. Pin care information should be given to patients who have an exfix. The protocol is to pour methylated spirited onto the pin 2x a day

Discharge

Has the patient received proper exfix pin care information?

Yes
 No

reset

Please instruct the patient on proper pin-care (pour methylated spirit onto the pin 2x a day)

Afterwards, change the answer to the above question to "Yes".

Has a follow-up schedule been generated for the patient?

* must provide value Yes
 No

reset

Please save this form as "Incomplete" and generate a follow-up schedule for the patient. Afterwards, change the answer to the above question to "Yes".

Time and Date of Discharge

* must provide value Insert date and time by clicking on the calendar image above

6.5 Follow-up Evaluation Form

This form is intended for use at all of the follow-up evaluations. These evaluations can be the Saturday in-person clinics or the ones done over the telephone in situations where the patient cannot come to clinic.

1. Follow-up visit number and type

- a. "Which follow-up evaluation?": Even though REDCAP automatically generates a new Follow-up Evaluation form at each evaluation time point, this form asks again what evaluation visit number this form is for. This is important because the questions for a 2 week visit are different from the 6 week to 1 year follow-up visit.
- b. It is important to properly answer the "Type of Follow-up Evaluation" question properly because what you say determines the types of questions that appear. Certain questions such as Range of Motion evaluation can only be answered in person.

Follow-up Visit	
Which follow-up evaluation? <small>* must provide value</small>	 2 Week  6 Week  3 Month  6 Month  1 Year <small>reset</small>
Record any reminders here to do for the patient during this follow-up visit: <small>Expand</small>	
Date of evaluation <small>* must provide value</small>	 <small>31</small>   Format is DD-MM-YYYY. Insert date manually, by clicking on the calendar image above, or press "Today" if applicable
Time from Surgery to Follow up	 
Type of Follow-up Evaluation **This is a key study question** <small>* must provide value</small>	 Patient attended Saturday clinic in-person  Telephone evaluation (missed clinic) <small>reset</small>
What is the reason for missing the appointment?	

2. Work

Return to Work		
Has the patient been working at all since the last follow-up visit?	 Yes  No	reset
Has their health status prevented them from going back to work?	 Yes  No	reset
Has their health status prevented them from working at their usual level?	 Yes  No	reset
Is this the first time the patient has gone back to work since the operation?	 Yes  No	reset
Estimated date of return to work?	   	D-M-Y
What is the type of employment for the patient's main source of income?	 Formal Employment  Informal Employment	reset
What type of duty does the patient perform as his or her main source of income?	 Heavy manual labor  Mostly walking but not heavy lifting  Mostly sitting or standing	reset
Approximately how much did the patient make per WEEK (in Tanzanian Shillings)?		
For approximately how many WEEKS did the patient work since the last follow-up visit	 <small>Report in weeks (not days or months)</small>	

3. Pain assessment

- 10 is always worst imaginable pain. 0 is always no pain.
- The Tegner-Lysholm Knee Scoring System questions will appear only for patients who report anterior knee pain. It is best to read out the answer choices for the patient rather than asking them to provide the answer and interpreting their response. While some of the questions repeat questions that have already been asked, the knee scoring system needs to be completed in its entirety in order for a score to be calculated from the responses the patient provides.

Pain Assessment

Mark all sites that are painful	 Knee  Fracture Site  Ankle/Foot  Other
Where in the knee is the pain the worst?	 Anterior  Posterior  Medial  Lateral
Current level of pain at the fracture sites?	
Specify other location of pain	
What is the patient's current level of pain today?	
Is there tenderness to palpation at the fracture site?	 Yes  No
Tegner-Lysholm Knee Scoring System: The following questions are specific to patients who have anterior knee pain.	
Is the anterior knee pain worse during weight bearing?	 Yes  No
Pain	 None  Inconstant during severe exertion  Noticeable during severe exertion  Noticeable after walking more than 2km  Noticeable after walking less than 2km  Constant
Does the patient have leg pain with weight bearing?	 Yes  No  N/A (Not weight bearing yet)
Instability	 Never giving way  Rarely (during severe exertion)  Frequently (during severe exertion)  Occasionally (in daily activities)  Often (in daily activities)  Every step

Limp	 None  Slight or periodical  Severe and constant	reset
Support	 None  Stick or crutch  Weight-bearing impossible	reset
Locking	 No locking/catching sensations  Catching sensation but no locking  Locking occasionally  Frequently  Locked joint on examination	reset
Swelling	 None  On severe exertion  On ordinary exertion  Constant	reset
Stair Climbing	 No problems  Slightly impaired  One step at a time  Impossible	reset
Squatting	 No problems  Slightly impaired  Not beyond 90°  Impossible	reset

4. Imaging and Functional Testing

- a. These questions all require physical examination by the patient's surgeon. These questions do not appear for patients who are being evaluated over the telephone
- b. A squat and smile test will be conducted like in the femur study. Be sure to upload the image with a clear view of the entire body during the test.

Imaging and Functional Testing

Maximum knee extension		
Maximum knee flexion		
Maximum ankle plantar flexion		
Maximum ankle dorsiflexion		
Is there a leg length discrepancy greater than or equal to 1cm?		 Yes, the operated leg is shorter  Yes, the operated leg is longer  No
		
How much is the leg length discrepancy in centimeters?		
This should be measured with a ruler with the patient lying down rather than approximated or self-reported by the patient)		
Is the operative limb malrotated compared to the unaffected side?		 Yes  No
		
Is the operated extremity internally or externally rotated?		 Internally rotated  Externally rotated
		
How big is the difference in rotation (in degrees)?		
Follow-up x-ray photos of operative site taken for this visit?		 Yes  No
* must provide value		
Is the patient able to go to a local hospital to take lateral and AP views of the operative site?		 Yes  No
		

Please have the patient take x-rays of the operative site. If, for some reason, no x-rays will be taken for this follow-up evaluation, please describe the reason here.		
* must provide value Expand		
Is the patient able to send a picture of him performing the squat and smile test? 
reset
 
  Yes  No 
		
Is the patient able to squat? 
reset
 
  Full squat (without pain)  Full squat (with pain)  Partial squat  Unable to squat 
		
Squat and Smile Photo Taken? 
reset
 
  Yes  No 
		
Please remember to upload the images on the image upload form.		
Squat and Smile Comments 
Expand
		

c. The walking test will be administered according to the NIH 4 Meter Walking Test guidelines. Two tests will be conducted, and REDCAP will automatically calculate the average. Directions can be found online at the following link:
<http://www.nihtoolbox.org/WhatAndWhy/Motor/Locomotion/Pages/NIH-Toolbox-4-Meter-Walk-Gait-Speed-Test.aspx>

Is the patient able to perform the walking speed test? 
reset
 
  Yes  No 
		
Walking Speed Test #1 (Seconds): 
Time to walk 4 meters (in seconds)
		
Walking Speed Test #2 (Seconds): 
Time to walk 4 meters (in seconds)
		
Averaged walking speed test time 
View equation
		

5. Complications

- a. Properly recording complications is critical for the study because our end goal is to compare complication and reoperation rates between the two groups.
- b. Exfix patients will have additional questions appear related to schanz pin tract infections

Exfix Questions

Has the patient been performing proper pin-care with spirit 2x a day?

Yes
 No

reset

Please inform the patient about the importance of proper pin care

What is the plan for the exfix?

(Removal at 3 months with or without cast applied is standard procedure)

Exfix removal at 3 months
 Exfix removal AND a cast will be applied
 Delayed exfix removal
 Other (early removal, conversion, etc.)

reset

This exfix plan is not standard. Please report this as a complication in the "Complications and Review" Form

Are the Schanz pin tracts infected?

Yes
 No
 N/A (Exfix already removed)

reset

How many pins are infected?

1 2 3 4

reset

Pin tract infection level (and corresponding treatment plan):

0 - Normal (requires weekly pin care)
 1 - Inflamed (requires daily pin care)
 2 - Serous discharge (requires antibiotics)
 3 - Purulent discharge (requires antibiotics)
 4 - Osteolysis (requires removal of pin)
 5 - Ring Sequestrum (requires debridement)

reset

Since surgery is required to fix the schanz pin infection, please record the details on the "Complications" Form

- c. If the patient has a medical or surgical complication, record "Yes" and proceed to the "Complications and Review" form. That is where additional information will be recorded.
 - i. A pop-up warning will appear if a patient has had a complication recorded and is coming back for follow-up. This is to enable us to be up to date with complications.

Complications

Does the patient have any complications? These can include:

- Infection
- Wound problems
- Nonunion/malunion
- Hardware failure
- Medical problems

* must provide value

Yes
 No

reset

Please record the complication in the "Complications and Review" form

This patient has previously had a complication recorded.

[figure not shown]
Please update the 'Complications' form with any new events that may have occurred since.

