Email: [contact]

1. Summary of Changes to Standard Operating Procedure

February 3, 2016 ([name])

Various items that required clarification arose after the first few weeks of the study. The following clarifications were agreed upon:

- **Damage Control:** Allowed (definitive treatment done within 2 weeks after first operation)
- **Exfix Pin-Care:** 2 weeks with dressing and BID pin wash with alcohol. Check at 2 week follow up. If dry, remove dressing. If discharge present, continue with dressing and additional evaluations before 6 weeks
- **Exfix Treatment:** 3 months then the following at surgeon's discretion to be documented in eval form (1) removal, (2) removal with cast, (3) delayed exfix removal, or (4) other. Delayed exfix removal or other will be submitted for adjudication review
- **Antibiotics:** 3 options at surgeon's discretion with (1) CTX, (2) CTX + gentamycin, (3) CTX + gentamycin + metronidazole
- **Weight Bearing Protocol (all patients):** 6 weeks toe touch then at surgeon's discretion
- **Nurses:** 2 per week (number of patients will increase next Saturday)
- **# IM Nail Interlocks:** 4 total on all nailed patients (2 prox, 2 distal)
- **Continue with study without interruption:** Yes
- **Cohort Study:** Will now include non-primarily closeable patients (we will attempt to contact the patients who came in since the start of the study)

There was also a patient "borderline" fracture who will be included and followed-up. We have made a note and can exclude during data analysis if necessary.

February 13, 2016 ([name])

Following the presentation of an open tibia patient approximately 3 days after their injury, a discussion occurred regarding whether or not an upper limit would be set for patients in the cohort study who present >24 hours post-injury.

- ➔ It was decided that there would be no upper limit.

April 6, 2016 ([name])

- ➔ It was decided that exfix patients who receive a cast will have the cast paid for by the study since it is a complication of their randomization (and not part of their typical treatment plan)
- ➔ [name] will send out a revised budget

April 10, 206 ([name])

[name] noticed during his site visit to MOI that there was underreporting of pin tract infections in the external fixation group. Previously, the question, "are the schanz pin tracts infected?" would only

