4.1 Outcomes

The primary outcome for our study will be composite, all-cause reoperation within one year of definitive skeletal stabilization, excluding bedside irrigation and debridement for superficial pin tract infections or planned ex-fix removal. The use of composite outcomes has been validated in a wide range of clinical trials.¹⁹ Primary events included in our composite outcome are detailed in the following table.

A participant who undergoes conversion from ex-fix to nail within six weeks of surgery will be analyzed according to the initial treatment that was assigned by randomization. Patients who undergo conversion from ex-fix to nail more than six weeks after the index procedure will be considered to have undergone a reoperation and will therefore count toward the primary outcome. Conversion from nail to ex-fix, regardless of time point, will be considered a primary outcome event.

Primary Events

Infection or hematoma	Repeat incision and debridement or drainage for superficial or deep infection or hematoma following initial wound healing.
Bone grafting	Bone grafting for patients > 6 months from index surgery. Bone grafting will be considered after 6 months in the case of delayed radiographic healing with > 2 months pain on attempted weight bearing.
Implant conversion (e.g. Ex Fix to IM nail) or implant exchange (e.g. exchange nailing)	Implant conversion or implant exchange > 6 months from index surgery to facilitate union.
Implant removal	
 1) For construct failure with appropriate clinical indication (broken hardware, half-pin failure at bone/pin interface). 2) Intramedullary nail removal to facilitate union. 3) Intramedullary nail removal due to patient reported pain or local irritation
Dynamization of intramedullary nail	
To facilitate healing > 6 months from index surgery.
 
* Note: Auto-dynamization without clinical indication for removal of broken component will not be counted as a primary event.

Osteotomy	To correct malalignment
Amputation	For limb salvage failure

Secondary clinical outcomes will include:

1. Post-operative compartment syndrome.
2. Superficial infection, as defined by CDC surveillance definitions, to include pin tract infections and cellulitis which resolves with use of antibiotics and local wound care.
3. Deep infection, as defined by CDC surveillance definitions, to include deep abscess or osteomyelitis.

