4.2 Sample Size

Data from two preliminary studies at MOI inform our projection for requisite statistical power. Our pilot study showed a difference in reoperation rate comparing external fixation and intramedullary nailing of 38% versus 3.8%, respectively. However, with longer follow-up and more stringent criteria for reoperation, we estimate a more conservative effect size is needed for power analysis. Therefore, to achieve 80% power (alpha=0.05) with a more conservative difference in the reoperation rate of 5% to 20%, the study would require 88 patients in each treatment group, or a total of 176 with completed follow up.

During the six month period from January to June 2012, MOI surgeons treated 238 patients presenting with open tibia shaft fractures, 50% (119) of whom suffered Gustilo Type 3A injuries - an incidence of approximately 20 patients per month. Our colleagues report the rate of open tibia fractures has continued to increase over the last two years and by current accounting, averages 25 patients with Gustilo Type 3A injuries per month. We therefore estimate an annual volume of approximately 300 qualifying injuries treated operatively at MOI. Assuming the majority meet inclusion criteria and a capture rate of 80%, we anticipate enrolling approximately 240 patients over a one year collection period. If the goal of 80% follow-up is met, a total of 192 patients will be included in our final analysis and we will achieve adequate statistical power. We will plan to conduct an interim analysis after six months to assess the accuracy of these initial estimates and determine whether the duration of the enrollment period should be altered.

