- 5. All patients will be contacted on the Wednesday prior to the Saturday clinic by phone as a reminder of the appointment time. A second reminder will be sent by text message on the day prior to the clinic.

No cash incentives will be provided to compensate for travel and other expenses. However, at the conclusion of 1 year, all patients who have been lost to follow up will be contacted by study staff to encourage return to the clinic. In cases where cost of travel is the principal barrier, a telephone follow-up evaluation will be conducted. The patient will also be asked to go to the nearest hospital, take follow-up x rays, and send in a picture of the x-rays. A picture of the patient performing the squat and smile test will also be requested.

5. 9 Study Financial Coverage

The following summarizes what is and what is not financially covered by the study. Any items not mentioned here need to be approved by the study review committee.

Covered	Not Covered

 - Ceftriaxone on admission - Ceftriaxone on subsequent surgeries that occur during the patient's first stay at the hospital - First dose of gentamycin * - First dose of metronidazole * - Consultation fees for follow-up clinics - Follow-up x ray images at 6k, 3mo, 6mo, 1yr - 2 week post-op control x-ray redo (if necessary) 	
 - Admission consultation and pre-op time - Cost of surgeries, implants ** - Post-op time in ward - Reoperations and all associated antibiotics and medications** - Exfix pin care methylated spirit - Knee brace - Physical therapy

* If the patient is not able to afford the remaining doses or has no relative who can purchase the antibiotics or will not be able to purchase the antibiotics in a timely fashion, these antibiotics will be provided for the patient at no extra cost

** While the study will not cover these items, the hospital may cover the cost if the patient is not able to afford

Study Steering Committee

The steering committee for the study will consist of [name], [name], [name], and [name]. The steering committee will be responsible for performing adjudication review, evaluating interim data, and approving any sub-projects.

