What is the surgical complication? <small>* must provide value</small>	 Superficial Surgical Site Infection  Deep Surgical Site Infection  Delayed Wound Healing  Nonunion/Delayed Union  Malignancy/Malunion  Hardware Failure (Non-infectious)  Missed Interlock  Compartment Syndrome  Other/Multiple 
Describe the details of the complication <small>* must provide value</small>	 
Upload any relevant images here (if available):	Upload document
Is reoperation being considered for this complication? <small>* must provide value</small>	 Yes  No 
Which hospital will the reoperation be performed at?	
ESTIMATED date of reoperation	   Format is DD-MM-YYYY. Insert date manually, by clicking on the calendar image above, or press "Today" if applicable

Has the reoperation been performed?

* must provide value

No
 Yes
 The patient no longer needs a reoperation

reset

This patient will now appear on the "Awaiting Reoperations" report. After the reoperation, change the answer to the above question to "Yes"

ACTUAL date of reoperation

Describe the reoperation that was performed:

Complication #1 Review

Has this issue been reviewed?

* must provide value

Yes
 No

reset

This issue needs to be reviewed.

Date of Review

Format is DD-MM-YYYY. Insert date manually, by clicking on the calendar image above, or press "Today" if applicable

Results of Review

* must provide value

- c. Additional surgical complications beyond the third event should be recorded in free text entry box. Label the event # accordingly (Event #4...)

Additional Surgical Complications

If the patient has had more than 3 surgical complications, describe them here. Include the following information:

1. Date complication first diagnosed by physician
2. Details of complication

If reoperation is being considered:

3. Type of surgery planned
4. Hospital
5. Estimated date of reoperation
6. Actual date of reoperation

[Expand](#)

Is reoperation being considered for any of these complications?

Yes
 No

* must provide value

[reset](#)

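### No follow-up item asks directly about a further operation on the leg, so events of the primary outcome can be missed

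*Protocol*

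**What the plan says.** Protocol 4.1 defines the primary outcome as "composite, all-cause reoperation within one year of definitive skeletal stabilization", apart from bedside care of superficial pin-tract infection and planned fixator removal. The listed primary events include "Intramedullary nail removal due to patient reported pain or local irritation".

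The follow-up form in 6.5 serves both clinic visits and telephone evaluations. It covers work, pain, knee score, motion, squat, walking speed, fixator questions and complications. The one mandatory complications item shared by both arms is "Does the patient have any complications? These can include", followed by five examples: infection, wound problems, nonunion or malunion, hardware failure and medical problems. A positive answer sends staff to the Complications and Review Form (6.6). There, within a surgical-complication event, the form asks "Is reoperation being considered for this complication" and then whether the operation has been done.

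External-fixation patients have two further items in 6.5, the fixator plan and the pin-tract grade. A non-standard plan triggers "This exfix plan is not standard. Please report this as a complication", and a pin infection needing surgery also leads to the Complications form. Nail patients have no matching item on the follow-up form.

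On the one-year contact, 5.8 says "In cases where cost of travel is the principal barrier, a telephone follow-up evaluation will be conducted". Section 6.5 allows a telephone evaluation whenever the patient cannot come to clinic.

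**The concern.** Reoperation is an event in the past. The item that opens the route to recording it asks about the present. A patient who was reoperated at another hospital between visits and is now well can correctly be recorded as having no complication, and the event is then not reached. The trial expects surgery elsewhere, because 6.6 asks which hospital will operate. The same form uses interval wording for work, asking about the time since the last visit, but not for the primary outcome.

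The trial has already met a similar problem. In the Summary of Changes (April 10 entry) a site visit found that "there was underreporting of pin tract infections in the external fixation group", because the question appeared only after another answer. The remedy was to ask it of every external-fixation patient at every visit. The primary outcome has no equivalent direct question.

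Two things are at stake. Equal loss of events in both arms shrinks the observed difference and costs power. Unequal loss distorts the comparison itself, and it is possible because the extra prompts exist in one arm only.

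**Working it through.** **The text.** The possible routes to a recorded reoperation, side by side:

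| Route | Where | What it leaves open |
|---|---|---|
| Present-tense complications item | 6.5, both arms | A past operation in a patient now well |
| Fixator-plan and pin-grade items | 6.5, external fixation only | Nail arm; weaker once the fixator is off, normally at 3 months, whereas grafting, implant exchange and dynamization count after 6 months (4.1) |
| Report outside clinic | 6.6 | Needs someone to volunteer it |
| Pop-up to update complications | 6.5, both arms | Only after an earlier recorded complication |
| Complications since discharge | 5.8, 2-week visit | Early events only |
| Examination and radiographs | 5.2, 5.8, 6.7 | Examination items are absent by telephone (6.5); films may be missing; a debridement may leave no implant change |

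No row is a direct question about surgery since the last contact.

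**The plan's own figure.** Inputs from 4.2: 5% against 20%, alpha 0.05, power 80%, 88 per arm. Taking alpha as two-sided:

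- n0 = [1.960 × √(2 × 0.125 × 0.875) + 0.842 × √(0.20 × 0.80 + 0.05 × 0.95)]² / 0.15² = 75.1.
- With continuity correction, n = (n0/4) × [1 + √(1 + 4/(n0 × 0.15))]² = 87.9, so 88.

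The stated 88 is reproduced and is not in dispute.

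**Sensitivity to missed events.** The protocol gives no capture rates, so 70-90% is an assumption. Observed rate = true rate × proportion captured. The test is the two-sided pooled z-test without continuity correction at 88 per arm:

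- SE0 = √(2p̄(1 − p̄)/88); SE1 = √((p1(1 − p1) + p2(1 − p2))/88).
- Rejection probability = Φ((d − 1.960 SE0)/SE1) + Φ((−d − 1.960 SE0)/SE1).

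Full capture: SE0 = 0.0499, SE1 = 0.0486, and (0.15 − 0.0977)/0.0486 = 1.077, so power is 85.9%. This exceeds 80% because the 88 carries a continuity correction and this test does not.

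*Equal capture in both arms, true rates 20% and 5%:*

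| Captured | Observed rates | Difference (points) | Power | Corrected n per arm |
|---|---|---|---|---|
| 100% | 20.0% / 5.0% | 15.0 | 85.9% | 88 |
| 90% | 18.0% / 4.5% | 13.5 | 81.5% | 100 |
| 80% | 16.0% / 4.0% | 12.0 | 76.0% | 113 |
| 70% | 14.0% / 3.5% | 10.5 | 69.6% | 131 |

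*No true difference, loss in one arm only:*

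| Captured in that arm | False-positive rate, true rate 20% | False-positive rate, true rate 10% |
|---|---|---|
| 100% | 5.0% | 5.0% |
| 90% | 6.3% | 5.6% |
| 80% | 10.6% | 7.5% |
| 70% | 18.4% | 11.0% |

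Example, 20% against 14%: (0.06 − 0.1110)/0.0564 = −0.903 gives 18.3%, and the other tail adds 0.1%.

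*True rates 20% and 5%, 80% captured in one arm only:* loss in the nail arm gives 20% − 4% = 16.0 points and 91.1% power. Loss in the external-fixation arm gives 16% − 5% = 11.0 points and 66.5% power.

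**The case against.** The strongest reply is that the complications item is not a patient questionnaire. Staff complete it in a clinic attended by a study investigator, with examination and two-view radiographs from 6 weeks on in both arms. Nail removal, exchange, conversion or amputation would usually be seen there. This stands for patients who attend and are filmed. It is weaker for telephone evaluations, where local films are requested but not assured, and for operations that leave the implant unchanged.

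The list of examples is also open-ended, pain is asked of everyone with a knee score for anterior knee pain, and the Complications form has a category for other events. So nail removal for pain can be recorded; it is simply not prompted.

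Known planned reoperations stay on a report until resolved. The April 22 change moved infections and wound complications to the Complications form and added a prompt at later visits for patients with an earlier complication. Both help with problems already on record, not with an event that was never entered.

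On asymmetry, the fixator prompts concern pins and the removal plan, much of which lies outside the primary outcome. The image form has more hardware items for nails (three) than for pins (two). This is a fair answer to any claim that the imbalance is established.

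On the telephone, 5.8 says everyone lost to follow-up is contacted at one year, and 6.5 is broader than 5.8 on who may be evaluated by telephone. What remains is that the two sections differ and should agree.

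**Conclusion.** The point holds as a gap in how the primary outcome is ascertained. No item in 6.5 asks directly about an operation since the last contact, and the remaining routes do not cover every case. Reoperations, especially at other hospitals, can be missed.

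A reader might infer three stronger things that the protocol does not support:

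- That the complications item is the only route to the outcome. It is not, as the list of routes shows.
- That the gap favours nailing. The prompts differ by arm, so unequal capture is possible, but they lose force after fixator removal, and nothing shows which arm would lose more events.
- That reoperations have in fact been lost. The documented under-reporting concerns pin-tract infection, and the log offers question ambiguity only as a possible cause.

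The figures are illustrations. They rest on assumed capture of 70-90%, 88 per arm and a two-sided pooled z-test. Under them, equal loss takes power from 85.9% to 81.5-69.6%. One-sided loss takes a nominal 5% false-positive rate to 6.3-18.4% (true rate 20%) or 5.6-11.0% (true rate 10%). Even equal loss is harmful, so the recommendation does not depend on asymmetry. Severity: recommended improvement.

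**What to change.** 1. Add one mandatory REDCap question to the follow-up form, in both arms, at all five visits and in telephone evaluations: *Since the last contact, has the patient had any operation on this leg, at any hospital? If yes: date, hospital, procedure, reason.*
2. Let a positive answer open the Complications and Review Form whatever the answer to the general complications item.
3. For patients already in follow-up, ask it once for the whole period since surgery.
4. Align 5.8 with 6.5, so that the question is put by telephone to every patient who misses the one-year visit, not only where travel cost is the barrier.

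The cost is one field, a short manual edit and a few minutes of staff time per contact, including some extra telephone answers. Treatment, eligibility and the outcome definition do not change.
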